6.13. Safety Analyses

The primary safety analysis will summarize treatment emergent ocular AEs (TEAE) separately for primary study eyes and secondary study eyes using discrete summaries at the eye and event level by system organ class and preferred term for each treatment group. A TEAE will be defined as occurring on or after the day treatment is initiated. Treatment emergent non-ocular AEs will be summarized using discrete summaries at the subject and event level by system organ class and preferred term for each treatment group. Treatment related treatment emergent ocular and non-ocular AEs will be summarized similarly. Treatment emergent ocular and non-ocular AEs will also be summarized by severity.

Slit lamp biomicroscopy and dilated fundoscopy measures will be summarized at each time point using discrete summary statistics.

Visual acuity data will be summarized at each time point using both continuous summaries, including change from baseline, and discrete summaries, including change from baseline in the number of lines and the proportion of subjects with a worsening of ≥ 3 lines from baseline. Ocular hyperemia and ocular comfort will be summarized at each time point using discrete summary statistics.

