All subjects will undergo follow-up visits at 2, 4, 6, 8, 10, and 12 Weeks. If at any visit, the Investigator deems it necessary to initiate IOP-lowering drops as rescue therapy due to an increase in IOP, the subject will be considered an efficacy failure and will be followed through the remainder of the study for safety. If still present, the intracanalicular depot will not be removed. IOP measurements taken through the remainder of the study will be excluded from the efficacy analyses.

For any subject, if at any point the intracanalicular depot is removed bilaterally by the Investigator for an adverse event or subject discomfort, the subject will be exited from the study at that visit. If the intracanalicular depot needs to be removed from only one eye, the depot from the contralateral eye will not be removed and the subject will be followed per the study schedule for safety.

Intracanalicular depots that are removed due to subject withdrawal or an undesired reaction at any point in the study will not be replaced.

For subjects with Early Loss of Intracanalicular Depot Prior to the 6 Week Visit:

At any visit prior to the 6 Week Visit, if the intracanalicular depot is not visualized in one or both eyes by the Investigator, the Investigator will insert a new intracanalicular depot in the respective eye(s) after confirming patency. For any depot replacements, IOP assessments should be completed prior to replacement. The subject will continue to return for follow-up visits per the study schedule through the 12 Week Visit. The number of depot replacements will be tracked and documented on the appropriate electronic Case Report Form (eCRF).

For subjects with Early Loss of Intracanalicular depot from the 6 Week Visit prior to the 12 Week Visit:

At any visit from the 6 Week Visit prior to the 12 Week Visit, if the intracanalicular depot is not visualized in one or both eyes by the Investigator, the Investigator will insert a new intracanalicular depot in the respective eye(s) after confirming patency. For any depot replacements, IOP assessments should be completed prior to replacement. The subject will return for follow-up visits through the 12 Week Visit and then at the 20 Week Visit. Depots replaced between the 6 Week Visit and the 12 Week Visit will not be

removed at the 12 Week Visit. The first attempt to remove these depots will be at the 20 Week Visit. The number of depot replacements will be tracked and documented on the appropriate eCRF.

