12 Week Visit:

If the intracanalicular depot(s) is/are still present at the 12 Week Visit, the Investigator will attempt to remove the depot(s). If removal is successful bilaterally, the subject will be exited from the study upon confirmation of the bilateral absence of the intracanalicular depot. If the intracanalicular depot are not present bilaterally at the 12 Week Visit, the subject will be exited at the end of that visit.

If removal is unsuccessful in one or both eyes at the 12 Week Visit, the subject will return at the 20 Week Visit. The subject may be prescribed IOP-lowering drops if necessary at the 12 Week Visit at the Investigator's discretion.

20 Week Visit:

At the 20 Week Visit, the Investigator will attempt removal of the intracanalicular depot(s), if still present. If removal at the 20 Week Visit is successful bilaterally, the subject will be exited from the study upon confirmation of the bilateral absence of the intracanalicular depot.

If removal at the 20 Week Visit is not successful in one or both eyes, the subject will be required to return to the clinic every 30 (\pm 10) days until the intracanalicular depot is confirmed to be no longer present or removal of the intracanalicular depot is successful for the respective eye(s). Removal will be attempted at every visit until the intracanalicular depot is no longer present.

The subject may be prescribed IOP-lowering drops if necessary at the 20 Week Visit at the Investigator's discretion.

Schedule of Visits and Assessments

The schematic of the study schedule is presented in Table 1, Table 2, and Table 3, respectively for: Stratum A, Stratum B, and Stratum C.

Table 1: Study Schedule for subjects on prostaglandin treatment at the time of the Screening Visit (Stratum A)

Study Parameter	Screening	Baseline Visit 1		Baseline Visit 2/ Insertion Visit		Follow-Up Assessments																
		6 weeks (-2 days/ +3 days) after Screening		2 days [+2 days] after Baseline Visit 1)		2 Week (Day 15 ±3 days)		4 Week (Day 29 ±3 days)		6 Week (Day 43 ±3 days)		8 Week (Day 57 ±3 days)		10 Week (Day 71 ±3 days)		12 Week (Day 85 ±3 days)		20 Week (Day 141 ± 7 days)				
		8AM	8AM	8AM	10AM	4PM	8AM	10AM	4PM	8AM	8AM	10AM	4PM	8AM	8AM	10AM	4PM	8AM	8AM	10AM	4PM	
Informed Consent	X																					
Determine Eligibility	X	X		X																		
Iris Color	X																					
Medical/Ophthalmic and Medication	X																					
Demographic Information	X																					

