Throughout the course of the study, all efforts will be made to remain alert to possible adverse events or untoward findings. If adverse events occur, the first concern will be the safety and welfare of the subject. Appropriate medical intervention will be undertaken. Any adverse events observed by the Investigator or reported by the subjects, whether or not ascribed to the study treatment, will be recorded on the subject's Adverse Event Case Report Form.

Documentation regarding the adverse event will be made as to the nature, date of onset, end date, severity, and relationship to study drug, action(s) taken, seriousness, and outcome of any sign or symptom observed by the physician or reported by the subject upon indirect questioning. All AEs will be coded using the MedDRA version 16.1.

AEs will be reported from the point subjects sign informed consent. The AE and treatment emergent adverse event (TEAE) reporting period ends upon study exit for new AEs. Existing AEs and TEAEs will be followed until:

- Resolution (return to baseline status or to 'normal')

- AEs may be determined to have resolved (completely) or resolved with sequelae.
- Principal Investigator determines, for events that do not end (i.e., metastasis), the condition to be chronic. The event can be determined to be resolved or resolved with sequelae.
- Stabilization of the event has occurred (no worsening expected by the investigator)

Adverse Event (or Adverse Experience, AE)

An AE is any untoward medical occurrence, which does not necessarily have to have a causal relationship with the treatment.

Adverse Ocular Event

An adverse ocular event is an AE that affects ocular tissues, the nasolacrimal duct, sinuses or vision. All adverse ocular events are a subset of adverse events.

Note: Subjects will be queried for the presence or absence of the following ocular complaints: excessive tearing, foreign body sensation, stinging/burning, and itching. Positive responses to these standardized ocular complaint inquiries should be reported as ocular complaints and not adverse ocular events unless the complaint: meets the criteria of a specific event as listed, and/or is: outside of normal limits, associated with clinical sequelae (e.g., adverse slit lamp examination findings), and requires an intervention to be resolved.

Treatment Emergent Adverse Ocular Event (or TEAOE)

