An adverse ocular event will be considered a treatment emergent AE if it occurs or worsens (based on severity: mild, moderate or severe) on or after the initiation of the intracanalicular depot insertion.

Treatment Emergent Adverse Event (or TEAE)

Treatment-emergent adverse events (TEAEs) are defined as any event that occurs or worsens on or after the initiation of the intracanalicular depot insertion, whether ocular or non-ocular in nature. Adverse events recorded in the eCRF which began prior to treatment will not be included in the summary tables but will be included in the AE data listings.

Adverse Reaction (or Related Adverse Event or Adverse Effect)

An adverse reaction is any noxious and unintended response to the treatment.

Unexpected Adverse Reaction (Unanticipated Adverse Effect)

An unexpected adverse reaction is an adverse reaction, the nature (including specificity and outcome) or severity of which is not consistent with the applicable product information. For this study, the study protocol; Investigator's Brochure; and prescribing information for the registered formulation of travoprost (Travatan®) will be used to assess events for unexpectedness.

Anticipated (as specified in the protocol) adverse ocular events that may be associated with OTX-TP or PV include, but are not necessarily limited to:

- Ocular hyperemia should be considered as an AE only if the subject complains of it or if the subject is discontinued because of ocular hyperemia
- Prostaglandin Associated Orbitopathy
- Iris discoloration
- Blepharitis
- Worsening in BCVA defined as ≥ 3 lines (≥ 15 letters)
- Subconjunctival hemorrhage
- Cataract
- Macular edema
- Conjunctivitis
- Keratitis
- Perforation of or trauma to the punctum and/or surrounding tissues
- Allergic reaction
- Chemosis
- Inflammatory reaction
- Epiphora, defined as clinically significant excessive tearing outside of normal limits
- Dacryocystitis
- Tearing with mucopurulent discharge
- Stenosis of the punctum
- Infection*

*Note: In the unlikely event of infection, the organism will be identified.

Serious Adverse Event (Serious Adverse Experience)

A serious adverse event (SAE) (experience) or reaction is any untoward medical occurrence that:

- results in death

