The expectedness of an AE should be determined based upon existing safety information about the study drug using these explanations:

- Unexpected: An AE or adverse reaction that is not listed in the study protocol, Investigator’s brochure, or prescribing information for the registered formulation of travoprost (Travatan®) or is not listed at the specificity or severity that has been observed.
- Expected: An AE that is listed in the Investigator’s brochure at the specificity and severity that has been observed.

AEs that are mentioned in the Investigator’s Brochure as occurring with a class of drugs or as anticipated from the pharmacological properties of the drug, but are not specifically mentioned as occurring with the particular drug under investigation are to be considered unexpected.

The Investigator should initially classify the expectedness of an adverse event, but the final classification is subject to the Medical Monitor’s determination.

AE Summaries

All AEs and TEAEs will be coded using MedDRA 20.0. AEs will be summarized in listings and tables for overall and ocular TEAEs by treatment group.

An overall summary will be presented that includes the number of AEs, TEAEs and the number and percentage of subjects who experienced at least one AE or TEAE, by treatment group and for all subjects. This summary will also include breakdowns of TEAEs further categorized as ocular (primary study eye and secondary study eye separately) or non-ocular, serious AEs (SAEs), ocular TEAEs by maximum severity, non-ocular TEAEs by maximum severity, related TEAEs, TEAEs leading to subject withdrawal, and deaths.

Additional summaries of TEAEs will be provided showing the number and percentage of subjects who experienced at least one TEAE and will be presented by SOC and PT. Non-ocular TEAEs will be summarized using discrete summary statistics and presented by treatment group at the subject and event level by SOC and PT. Ocular TEAEs will be similarly summarized at the subject level for both eyes and for primary study and secondary study eyes separately. If a subject reports the same PT multiple times within the same SOC, that PT will only be reported once within that SOC. As with the PT, if a subject reports multiple conditions within the same SOC, that SOC will only be reported once. In the summary, SOC will be listed in ascending alphabetical order; PTs will be listed in order of descending frequency for all subjects within each SOC.

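### TEAE percentages by arm pool 12-week with 20-week-or-longer follow-up, set by depot events after randomisation, and no AE table has a common cut-off

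*SAP*

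**What the plan says.** **Window.** SAP v2.0 Section 14 (Ocular and Non-Ocular Adverse Events) defines a TEAE as "any event that occurs or worsens on or after the initiation of the intracanalicular depot insertion". Protocol 6.13 has the same starting point: "A TEAE will be defined as occurring on or after the day treatment is initiated". The window has no fixed closing day: "The AE and treatment emergent adverse event (TEAE) reporting period ends upon study exit for new AEs".

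**Exit.** SAP v2.0 Section 4 makes exit depend on the depot.
- Depots removed at Week 12: "If removal is successful bilaterally, the subject will be exited from the study upon confirmation of the bilateral absence of the intracanalicular depot".
- Depots already gone: if they are "not present bilaterally at the 12 Week Visit, the subject will be exited at the end of that visit".
- A depot replaced from the 6 Week Visit on, before Week 12: "The subject will return for follow-up visits through the 12 Week Visit and then at the 20 Week Visit".
- Failed removal at Week 12 also leads to the 20 Week Visit. Failed removal at Week 20 leads to visits about every 30 days until the depot is gone.

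**Drops.** For subjects who go on after a failed removal, the same section adds: "The subject may be prescribed IOP-lowering drops if necessary at the 12 Week Visit at the Investigator's discretion".

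**Summaries.** The AE Summaries part of Section 14 plans: "Additional summaries of TEAEs will be provided showing the number and percentage of subjects who experienced at least one TEAE". These are by arm on the Safety population, with event-level counts for some categories. Neither the text nor the AE table titles in Section 22 give a Week 12 cut-off, a person-time rate or a time-to-event method. Protocol 6.13 names the ocular TEAE summary as the primary safety analysis.

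**The concern.** A percentage of subjects with at least one event has a clear meaning only over a stated period. Here the period differs between subjects, and what lengthens it (late depot loss or failed removal) happens after randomisation. The figure is neither a 12-week nor a 20-week risk. It is a mixture of the two, with weights set by depot events.

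Two consequences follow. First, if late replacement or failed removal is more frequent in one arm, that arm has more time in which to record events, and its percentage rises without any drug effect. Second, time after Week 12 is seen only in a subset selected by depot history. Those subjects may have started IOP-lowering drops at Week 12, yet their later events still count toward the randomised arm. That can blur the contrast even when both arms extend equally often.

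The SAP uses a 12-week boundary elsewhere: for unscheduled-visit data (Section 9) and for one set of replacement summaries (Section 13.1.3). It does not use one for AEs.

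**Working it through.** The plan gives no AE risk and no share of subjects extended, so there is no figure of its own to reproduce on this point.

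**Inputs from the documents.** Insertion is Day 1, the 12 Week Visit is Day 85 and the 20 Week Visit is Day 141 (protocol 4.5.7.9). Planned sizes are 330 and 220.

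**Assumptions.** The 12-week TEAE risk r is taken as 5% to 40%. The share f of an arm followed to Week 20 is varied. The hazard is constant and equal in both arms, so the true difference is zero. Visits beyond Week 20 and exits before Week 12 are ignored.

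**Step 1, time at risk.** 85 − 1 = 84 days against 141 − 1 = 140 days. The ratio is 140/84 = 1.67, and the excess is 56 days.

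**Step 2, risk for an extended subject.** R = 1 − (1 − r)^(140/84). For r = 20%, R = 1 − 0.80^1.667 = 31.1%, a gain of 11.06 points.

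**Step 3, crude percentage in an arm.** (1 − f)·r + f·R = r + f·(R − r). At r = 20%:
- f = 10%: 21.1%
- f = 20%: 22.2%
- f = 30%: 23.3%
- f = 50%: 25.5%

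**Step 4, spurious difference between arms.** (f₁ − f₂)·(R − r), so only the gap in shares matters. The sampling standard error (SE) of the difference is √[r(1 − r)(1/330 + 1/220)]. At r = 20% this is √(0.16 × 0.007576) = 3.5 points.

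| r | R | R − r (points) | 10-point gap | 20-point gap | 30-point gap | SE (points) |
|---|---|---|---|---|---|---|
| 5% | 8.2% | 3.19 | 0.3 | 0.6 | 1.0 | 1.9 |
| 10% | 16.1% | 6.10 | 0.6 | 1.2 | 1.8 | 2.6 |
| 20% | 31.1% | 11.06 | 1.1 | 2.2 | 3.3 | 3.5 |
| 40% | 57.3% | 17.32 | 1.7 | 3.5 | 5.2 | 4.3 |

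The sign follows whichever arm is extended more often. At r = 20%, OTX-TP minus PV is −2.2 points with shares of 10% and 30%, and +2.2 points with 30% and 10%.

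**Step 5, equal shares.** With f₁ = f₂ the difference is 0.0 points. At 20% extended in both arms, each would show 22.2%, which is still not a 12-week risk.

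**Step 6, common cut-off.** With onset limited to the 12 Week Visit, both arms show r under this model whatever the shares, so the spurious difference is 0.

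The blurring by drops started at Week 12 is not quantified. The documents give neither the number of subjects who would start them nor the event rate on them.

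**The case against.** The strongest reply is that nothing in the documents says the arms will be extended at different rates. Protocol 3.3.2 describes the placebo depot as identical except for travoprost. A reader might infer that the arms are certain to have unequal follow-up, or that most subjects exit at Week 12. The documents support neither inference. Unequal follow-up between subjects is built into the design; between arms it is conditional, and no share is given. This part of the reply stands.

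The SAP would also expose an imbalance. Section 10 tabulates exits before Week 12, at Week 12, at Week 20 and later, by arm. The Treatment Exposure text summarises days by arm, Table 14.2.4.2 summarises replacements, and AE onset dates are recorded. That stands as disclosure. It does not adjust the AE percentages, and the exposure variable cannot serve as their denominator: for completed or discontinued subjects it stops at the last visualisation of a depot, not at exit.

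AE reporting is descriptive, with no test or success rule, and the illustrative distortions at r = 20% are below one SE. A constant hazard is also doubtful, since procedural events may cluster around insertion. These points limit the importance of the matter.

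A reader might also take the first 12 weeks as complete and free of drops, and so want Week 12 to replace the full-period tables. That goes too far. Rescue drops are allowed earlier, bilateral removal for an AE or discomfort ends participation early, and the plan allows for 10% discontinuation before Week 12. Depots replaced from Week 6 stay in place past Week 12, and the product is described as releasing drug for up to about 90 days. Late events in those subjects can be on-treatment events and belong in a main table.

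**Conclusion.** The point holds in a limited form. TEAE percentages by arm mix 12-week follow-up with follow-up to Week 20 or beyond, and the mix is set by depot events after randomisation. Whether this distorts the arm comparison depends on those events differing by arm, which the documents neither state nor exclude. If they do differ, a 10- to 30-point gap in the share extended gives a spurious difference of about 1 to 3 points, in either direction. That range assumes a 20% 12-week risk, a constant equal hazard and extension to Week 20 only; the size changes with the risk as tabulated. With equal shares this distortion is zero. What remains then is a percentage without a defined period, and possible blurring by events in subjects who started drops at Week 12. The planned exit and exposure tables would show an imbalance, but the AE tables would not account for it. This is a cheap improvement to reporting, with no bearing on the primary efficacy analysis.

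**What to change.** In SAP v2.0 Section 14 (AE Summaries) and Section 22:

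1. Keep the full-period TEAE tables as planned.
2. Add versions of the overall, ocular and special-interest summaries (Tables 14.3.2.1, 14.3.2.2.2 and 14.3.2.2.9) by arm, limited to onset from first insertion through the subject's 12 Week Visit or earlier exit.
3. Add a table by arm of TEAEs with onset after the 12 Week Visit, with the number of subjects followed beyond Week 12 as denominator.
4. Optionally add a rate per person-time from insertion to exit. This also helps with unequal follow-up from early exit, which a Week 12 cut does not remove.

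One passage needs reconciling first. SAP Section 4 sends every subject with a late replacement on to Week 20, but also exits subjects with no depot in either eye at Week 12. The exit time of a late-replaced subject whose depots are gone by Week 12 is therefore unclear, and the follow-up counts depend on it.

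The cost is SAP wording, one onset-date flag and a few extra tables. Readers will have more than one AE table to compare. No event is removed from the full-period tables or listings.

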4.5.7.9. Follow-up Assessments

4.5.7.9.1. 4 Week (Day 29± 3 days), 8 Week (Day 57 ± 3 days), and 10 Week (Day 71 ± 3 days) Visits

The following will be performed for both eyes:

At 8AM only

- Medication and medical history update
- Subject ocular comfort assessment
- Assessment of Ocular complaints
- Assessment of BCVA
- Slit lamp biomicroscopy
- Assessment and grade of ocular hyperemia (at slit lamp)
- Confirmation of intracanalicular depot presence by the Investigator
- Punctum exam
- IOP measurement
- Adverse event assessment

*If the intracanalicular depot has to be removed for subject discomfort or an undesirable reaction, the investigator will prescribe IOP lowering medication at his/her discretion, and the subject will be exited from the study.

4.5.7.9.2. 2 Week (Day 15 ± 3 days) and 6 Week (43 ± 3 days) Visits

The following will be performed for both eyes:

At 8AM (T₀)

- Medication and medical history update
- Subject ocular comfort assessment
- Assessment of Ocular complaints
- Assessment of BCVA
- Slit lamp biomicroscopy

• Assessment and grade of ocular hyperemia (at slit lamp)

• Confirmation of intracanalicular depot presence by visual assessment

• Punctum exam

At 8AM (T₀), 10AM (T₀+2h) and 4PM (T₀+8h)

- IOP measurement
- Adverse event assessment

At any visit prior to the 6 Week Visit, if the intracanalicular depot is not visualized in one or both eyes by the Investigator, the Investigator will insert a new intracanalicular depot in the respective eye(s) after confirming patency. For any depot replacements, IOP assessments should be completed prior to replacement. The subject will continue to return for follow-up visits per the study schedule through the 12 Week Visit. The number of replacements will be tracked and documented on the appropriate Case Report Form (CRF).

If the intracanalicular depot is still present in one or both eyes at the 12 Week Visit, the Investigator will attempt to remove the intracanalicular depot from the respective eye(s). If removal is successful bilaterally, the subject will be exited from the study. The subject may be prescribed IOP-lowering drops at the Investigator's discretion.

If removal is unsuccessful in one or both eyes, the subject will return at the 20 Week Visit. The subject may be prescribed IOP-lowering drops at the Investigator's discretion.

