Separate summaries will be provided for the following categories of AEs:

- Ocular TEAEs in the primary study eye
- Ocular TEAEs in the secondary study eye
- Non-ocular TEAEs
- Expected TEAEs
- Unexpected TEAEs
- Treatment related ocular TEAEs
- Treatment related non-ocular TEAEs
- Serious AEs
- TEAEs by Maximum Severity
- Non-related TEAEs by Most Likely Cause
- Non-related SAEs by Most Likely Cause
- Ocular TEAEs of Special Interest

The following Preferred Terms are considered TEAEs of Special Interest:

- Conjunctival hyperaemia
- Ocular hyperaemia
- Iritis
- Cystoid macular oedema
- Eye colour change

- Madarosis
- Eyelash discolouration
- Eyelash hyperpigmentation
- Eyelash injury
- Growth of eyelashes

All TEAEs, SAEs and TEAEs leading to subject withdrawal from the study will be presented in subject listings separately for ocular and non-ocular events.

Best Corrected Visual Acuity (BCVA)

The logarithm of the minimum angle of resolution (logMAR) visual acuity is assessed at each visit using an EDTRS chart at a viewing distance of 4 meters. BCVA will be measured without refraction using a pinhole or while the subject is wearing his/her glasses, if the subject normally wears glasses or contact lenses. Subjects are required to read the chart from the top to the bottom until 2 letters are misread on the line. The visual score is to be calculated based on an assigned value of 0.02 logMAR per letter. If visual acuity is so poor that the subject cannot read any of the largest letters at 4 meters, then acuity is to be measured at 2 meters and the appropriate conversions made.

If visual acuity is so poor that the subject cannot read any of the largest letters at 2 meters, the subject should be checked for the ability to count fingers or see hand motion or light perception as appropriate.

BCVA will be measured at screening, at 8AM on Baseline Visit 2 and as well as the 8AM time point at each post-baseline visit. The baseline measurement will be the last assessment prior to insertion of the depot.

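### Hyperaemia that costs one eye its depot is not an AE if the subject neither complained nor was discontinued, so it misses the TEAE and special-interest tables

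*SAP*

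**What the plan says.** Protocol 5.5.1 and SAP version 2.0, section 14 (list of anticipated ocular events), carry the same sentence: "Ocular hyperemia should be considered as an AE only if the subject complains of it or if the subject is discontinued" on account of it. Grade, treatment and depot removal are not triggers.

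On removal from one eye, SAP section 4 (General Study Design) says the "depot from the contralateral eye will not be removed and the subject will be followed per the study schedule for safety"; Protocol 4.6 says the same. The footnote in Protocol 4.5.7.9.1 (4, 8 and 10 Week Visits) differs. If a depot is removed for discomfort or an undesirable reaction, the investigator will "prescribe IOP lowering medication at his/her discretion, and the subject will be exited from the study", and no exception is made for a single eye.

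On complaints, SAP section 14 states: "Subjects will be queried for the presence or absence of the following ocular complaints: excessive tearing, foreign body sensation, stinging/burning, and itching". Redness is not among the four. SAP 13.1.4 adds an Other Ocular Complaints category. Protocol 4.5.7.6.3 tells subjects at discharge to contact the study doctor if redness increases.

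Under AE Summaries, SAP section 14 says: "The following Preferred Terms are considered TEAEs of Special Interest". Conjunctival hyperaemia and ocular hyperaemia are the first two terms listed. They are reported in Table 14.3.2.2.9.

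**The concern.** The second trigger in the hyperaemia rule works at subject level, while the product is inserted and removed per eye and SAP section 9 presents ocular AEs per eye. Losing a depot to hyperaemia is a change in management, but when it happens in one eye the rule does not recognise it.

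The special-interest table was added in SAP version 2.0 at the sponsor's request, while the rule that decides what may enter it stayed as in version 1.0. Protocol 3.1 names conjunctival hyperaemia among the limitations of travoprost drops, and Protocol 4.7.1 lists ocular hyperaemia as a study risk, so a difference between arms is plausible. An event that fails the rule receives no severity or relatedness rating as an AE.

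The rule also sits awkwardly beside the general instruction in SAP section 14: "Any adverse events observed by the Investigator or reported by the subjects, whether or not ascribed to the study treatment, will be recorded". For hyperaemia, the investigator's own observation is not enough unless the subject is discontinued.

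**Working it through.** The point depends on no sample size, power or rate, so there is no figure in the plan to reproduce. The check is a reading of the rules against each possible case of hyperaemia seen at the slit lamp.

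| Case | Complaint trigger | Discontinuation trigger | AE? |
|---|---|---|---|
| Subject complains, whatever is done next | met | not needed | yes |
| No complaint, both depots removed, subject exits because of it | not met | met | yes |
| No complaint, one depot removed, read with Protocol 4.6 and SAP section 4 | not met | not met: subject stays in follow-up | no |
| No complaint, one depot removed, read with Protocol 4.5.7.9.1 | not met | met: subject exits | yes |
| No complaint, treated, no removal, subject continues | not met | not met | no |
| No complaint, no action | not met | not met | no, as the rule appears to intend |

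Three things follow.

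1. The gap is the third and fifth rows. Each needs three conditions together: no complaint, an action (one-eye removal or treatment), and no discontinuation.

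2. The third and fourth rows describe the same event with opposite answers, depending on which exit passage a site follows. The passages must be reconciled.

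3. Special-interest events are a subset of TEAEs, so an event that is not an AE is absent from Table 14.3.2.2.9 and also from the ocular TEAE tables (14.3.2.2.2 to 14.3.2.2.5).

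What is still reported for such a case: grade and shift by visit and eye (Tables 14.3.7.1 and 14.3.7.2); the removal and its reason (Table 14.2.4.3, Listing 16.2.5.4); and any ocular medication (Table 14.1.6.2, Listing 16.2.4.8). None of these outputs is specified to connect the grade with the removal or the medication.

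**The case against.** The case against is substantial, and most of it stands.

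- A reader might infer that all treated hyperaemia, or all hyperaemia leading to one-eye removal, is kept out of the AE tables. The documents do not support that. Any hyperaemia the subject complains of is an AE, whatever follows.
- Complaints have several routes: the discharge instruction on redness, the open complaint category asked about at each post-baseline visit, and AE assessment at every scheduled visit. Hyperaemia bad enough to cost a depot, in a subject told to report redness who says nothing, may be uncommon.
- The treatment case is narrow. Protocol 4.5.7.8 prohibits non-diagnostic topical ophthalmic solutions from Baseline Visit 1, apart from limited use of tears or lubricants. Protocol 5.5 asks for the diagnosis in place of the symptom, and conjunctivitis, keratitis, allergic reaction and inflammatory reaction are listed in 5.5.1 without the restriction.
- On Protocol 4.5.7.9.1 alone, a one-eye removal would lead to exit and so to an AE.
- Grades are collected whatever the AE status and reported by arm, so an excess in grade would be visible.
- A reader might see a clash with the removal form, which offers AE as a reason. There is none: SAP section 12 (Intracanalicular Depot Removal) also allows the reason other, and such a removal can be coded there.
- A reader might multiply an assumed 1% to 3% by the planned 330 OTX-TP subjects (330 × 0.01 = 3.3; 330 × 0.03 = 9.9). The documents give no rate, so this is not evidence of size.

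What the objection does not remove is the mismatch of level. On Protocol 4.6 and SAP section 4, removal of both depots meets the rule through exit and removal of one does not, though the clinical finding in the eye may be the same.

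**Conclusion.** A narrow gap in the AE rule stands, and it is minor. Investigator-observed hyperaemia that leads to removal of one depot, or more rarely is treated, falls outside the AE definition when the subject neither complained nor was discontinued, and so is absent from the TEAE and special-interest tables. For one-eye removal, this assumes that sites follow Protocol 4.6 and SAP section 4 and not the footnote in Protocol 4.5.7.9.1. For treatment without removal, the exit conflict does not matter.

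The number of subjects is unknown and may be small or zero. It is tempting to conclude that Table 14.3.2.2.9 understates drug-related hyperaemia in the OTX-TP arm. The documents support only a risk of that: the rule applies equally to both masked arms, and no rate of uncomplained, acted-upon hyperaemia is given. The primary efficacy analysis is not affected.

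**What to change.** Extend the second trigger to eye level in Protocol 5.5.1 and SAP section 14, for example: hyperaemia is an AE only if the subject complains of it, or if it leads to depot removal in either eye or to discontinuation of the subject. Hyperaemia without a complaint or a trigger stays in the grade and shift tables, as now. Separately, reconcile the exit rule in Protocol 4.5.7.9.1 with Protocol 4.6 and SAP section 4, so that the same removal is classified the same way at every site.

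The SAP repeats a protocol recording rule, so a SAP edit alone cannot create severity or relatedness ratings that were never collected. If AE collection is already complete, leave the rule and add one listing, by eye, joining hyperaemia grade with depot removals (with reason) and ocular medications. It uses data already collected and also shows the treated cases that the revised trigger would not reach.

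The cost is one clause in two documents and in the eCRF guideline, or one listing. The downside of the clause is a few more hyperaemia AEs and, if made mid-study, some inconsistency in ascertainment over time, which the study report should state.
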